5. GENERAL METHODOLOGY AND CONVENTIONS

5.1. Hypotheses and Decision Rules

There are no statistical hypotheses or statistical decision rules for PK and safety data.

5.2. General Methods

To assess any effect of PF-06650833 on EE or LN exposures, natural log transformed AUC_{last} and C_{max} will be analyzed using a mixed effects model with treatment as a fixed effect and participant as a random effect. Estimates of the adjusted mean differences (Test-Reference) and corresponding 90% CIs will be obtained from the model and will be exponentiated to provide estimates of the ratio of adjusted geometric means (Test/Reference) and 90% CIs for the ratios.

The following assessment should be performed:

- Effect of PF-06650833 on OC (EE or LN) exposures with OC alone (Period 1 Day 1 PK) as the Reference treatment and co-administration of PF-06650833 and OC (Period 2 Day 10 PK) as the Test treatment.*

Data will be presented – ie, listed and summarized – by treatment/period and overall. Continuous data will be summarized comprising mean, median, standard deviation, minimum and maximum. Categorical and binary data that are summarized will be via percentages. Some measures will be summarized using graphical representations by treatment/period, where appropriate.

The assignment of the reference and test treatment for drug-drug interaction evaluation is shown in Table 4.

Table 4. Assignment of Reference and Test Treatments

Reference Treatment (Observation Time)	Test Treatment (Observation Time)
OC (EE+LN) (PERIOD 1/DAY 1)	PF-06650833 + OC (EE+LN) (PERIOD 2/DAY 10)

Table 5. Calculation and Safety Reporting by Treatment

Treatment Code	Treatments	PK Calculation	Safety reporting
R	OC (EE and LN)	Day 1 PK in Period 1	Period 1
T	OC (EE and LN) + PF-06650833	Day 10 PK in Period 2	Period 2

For summary statistics, median and mean plots by sampling time, the nominal PK sampling time will be used, for individual participant plots by time, the actual PK sampling time will be used.

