3.4. Baseline Variables

The following baseline variables will be summarized for each treatment. Details of summary analyses are described in [Section 6](#).

Demographic characteristics:

- Baseline age.
- Gender (female vs. male).

- Race (white, black, Asian, other).
- Baseline body weight.
- Baseline Body Mass.

The baseline data measured at Day 1 are:

- Medical history & demography, medication history.
- Physical Examinations.

For laboratory data, baseline for the "PF+OC" phase is defined as the last measurement collected before administering the first dose of OC at the beginning of Period 2 (ie, P2D10 pre-dose).

For vital signs data, baseline for the "PF-only" phase is defined as the last measurement collected before administering the first dose of PF at the beginning of Period 2 (ie, P2D1 pre-dose), and baseline for the "PF+OC" phase is defined as the last measurement collected before administering the first dose of OC at the beginning of Period 2 (ie, P2D10 pre-dose).

For ECG data, baseline for the "PF+OC" phase is defined as the last measurement collected before administering the first dose of OC at the beginning of Period 1 (ie, P1D1 pre-dose).

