3.5.1. Adverse Events

An adverse event will be considered a Treatment-Emergent Adverse Event (TEAE) if the event started during the effective duration of treatment. All events that start on or after the first dosing day and time/start time, if collected, but before the last dose plus the lag time (28 days) will be flagged as TEAEs. The algorithm will not consider any events that started prior to the first dose date. Any events occurring following start of treatment or increasing in severity and occur in either of the following three phases: OC, PF-06650833 (Days 1-10 of

Period 2), OC+PF-06650833 (Days 10-12 of Period 2), will be counted as treatment emergent. Events that occur in a non-treatment period (for example, Follow-up) will be counted as treatment emergent and attributed to the previous treatment taken.

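### SAP Table 5 has no PF-only row for safety, in conflict with the PF-only phase in SAP 3.5.1 and 3.4, and the 3.5.1 phases overlap on Day 10

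*SAP*

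**What the plan says.** SAP 5.2 requires data to be shown "by treatment/period and overall". Its Table 5, titled "Calculation and Safety Reporting by Treatment", then has a safety column with two entries: code R (OC) is Period 1, and code T (OC + PF-06650833) is Period 2. The design table in SAP 2.2 (Table 2) uses the same two codes and describes T as nine days of PF-06650833, the OC tablet on Day 10, and PF-06650833 through Day 11.

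SAP 3.5.1 works with three phases. The first two are introduced with "occur in either of the following three phases: OC, PF-06650833 (Days 1-10 of", where the days meant are those of the second period. The third is given as "OC+PF-06650833 (Days 10-12 of Period 2), will be counted as treatment emergent". On timing it says: "All events that start on or after the first dosing day and time/start time, if collected".

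SAP 3.4 also separates the two parts of Period 2. Its vital-sign entry on PF-only reads: "phase is defined as the last measurement collected before administering the first dose of PF at the beginning of Period 2 (ie, P2D1 pre-dose". On PF+OC, its entries on vital signs and on laboratory data both point to this reading: "last measurement collected before administering the first dose of OC at the beginning of Period 2 (ie, P2D10 pre-dose". ECG has a PF+OC baseline only, which precedes this dose: "first dose of OC at the beginning of Period 1 (ie, P1D1 pre-dose".

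SAP 6.2.3 summarises and plots vital signs by treatment. SAP 6.2.1 refers adverse-event reporting to the sponsor's standards and gives no column layout.

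**The concern.** The only secondary objective is the safety of PF-06650833 when given together with the OC. Table 5 labels Period 2 safety as that combination, yet most of Period 2 is PF-06650833 alone. The endpoint sections split the period and the reporting table does not, and nothing ranks one over the other. Two programmers could follow the same SAP and produce different safety tables: one with two columns, in which PF-only events appear as co-administration events, and one with three.

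The three-phase text has a gap of its own. Its two Period 2 phases both include Day 10, the day of co-administration, so an event on that day fits both.

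**Working it through.** No figure in the plan is to be reproduced here. The check sets the sections side by side and counts from the schedule.

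**Schedule** (SAP 2.2; Protocol 1.3, Schedule of Activities). Period 2 runs from Day 1 to Day 12. PF-06650833 is given on Days 1 to 11 and the OC on Day 10. Cross-check: Day -1 (1 day) + Period 1 (3 days) + Period 2 (12 days) = 16 days and 15 nights, which matches the stated stay.

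**Share of Period 2 before the OC dose.**
- Days: 9/12 = 75%.
- PF-06650833 doses: 9/11 = 82%.

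**What Table 5 does with that time.** SAP 3.4 describes both P2D1 and P2D10 as the beginning of Period 2, so two readings are possible.
- If Period 2 in Table 5 means all 12 days, PF-only events are labelled OC + PF-06650833.
- If it means Day 10 onward, PF-only events have no row.

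Neither reading gives the three phases of SAP 3.5.1.

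**Day 10.** Days 1-10 are 10 days and Days 10-12 are 3 days. 10 + 3 = 13 phase-days for a 12-day period, and the surplus day is Day 10, which is one of the three OC+PF days. An event on that day is treatment-emergent either way; only its phase is open. The attribution rule at the end of 3.5.1 covers non-treatment periods such as follow-up, so it does not settle the matter.

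**Vital signs.** As the Schedule of Activities reads, Period 2 vital signs fall on Days 1, 10 and 12. Footnote e places them before dosing, and no dose is given on Day 12. The Day 10 reading is therefore the only scheduled one after PF-06650833 starts and before the OC. SAP 3.4 makes it the PF+OC baseline. SAP 3.5.3 takes minima, maxima and largest changes over all post-dose readings. Under Table 5, a Day 10 reading that follows nine PF-06650833 doses could count as a post-dose value of T. With P2D10 as baseline, its own change would be

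P2D10 - P2D10 = 0,

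so T's largest increase would become max(0, D12 - P2D10) instead of D12 - P2D10. A participant whose value fell would show 0, although 3.5.3 asks for the smallest decrease. T's absolute minimum and maximum would also include a PF-only value.

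**Laboratory data and ECG.** Scheduled Period 2 laboratory tests are on Days 9, 11 and 12. Day 9 is the last before the OC and so serves as the PF+OC baseline; Days 11 and 12 follow the OC. Scheduled Period 2 ECGs are on Days 11 and 12, both after the OC. Scheduled post-baseline readings mislabelled: 0 of 2 for each.

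**The case against.** Table 5 agrees with the SAP's own design table, where T is the whole Period 2 regimen. On that view it is coarser than SAP 3.5.1 but not mistaken. SAP 5.2 is general, while 3.4 and 3.5.1 are specific, and a careful programmer would let the specific text win. Both points are fair, and the second probably describes what would happen. They do not remove the conflict: Table 5 has its own safety column, it labels T as the combination, and no sentence gives precedence.

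Four stronger readings might be inferred, and the documents do not support them.
- *PF-only events will certainly appear under co-administration.* SAP 6.2.1 leaves the layout to sponsor standards that are not reproduced, so this follows only from Table 5 and the by-treatment/period rule taken literally.
- *T has two competing vital-sign baselines.* It does not. SAP 3.4 ties P2D10 pre-dose to PF+OC, which is T's label, and keeps P2D1 for PF-only. What remains open is whether the P2D10 value is also counted as a T post-dose value.
- *Table 5 contradicts the Safety set in SAP Table 3.* Its clause about the product taken is analysis-set wording; it does not allocate events to phases within a period.
- *An untimed Day 10 event cannot be placed at all.* SAP 5.3 applies the sponsor's imputation rules to safety data, and these may cover missing start times. All that can be said is that the SAP text states no cut. Participants are confined and dosing is supervised, so such events should be few.

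**Conclusion.** Wrong as written, minor in severity. Table 5 states a safety-reporting rule that, followed literally, conflicts with the phases in SAP 3.5.1 and the vital-sign baselines in 3.4. The 3.5.1 phases also overlap on Day 10.

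The 75% and 82% are shares of days and doses, not of adverse events; the documents give no event rates from which to estimate a count. The effect on adverse-event columns is an inference, and the vital-sign effect rests on the Schedule of Activities as it reads in the extracted table. Unscheduled readings on the PF-only days could add to it.

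The reach is limited to descriptive adverse-event and vital-sign summaries and plots in about 10 participants. SAP 5.1 sets no hypotheses or decision rules, and participant listings under SAP 6.2 keep individual events traceable. The primary PK comparison (Period 1 Day 1 against Period 2 Day 10), the scheduled Period 2 ECGs and the post-baseline laboratory tests are unaffected.

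**What to change.** Edit the SAP as follows.

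1. Add a PF-only row to the safety column of Table 5, from the first PF-06650833 dose on P2D1 to just before dosing on P2D10. Restrict the OC + PF-06650833 row to P2D10 dosing onward.
2. State that the phases in 3.5.1 and 3.4 govern the adverse-event and vital-sign tables and plots.
3. In 3.5.1, cut the PF-only and PF+OC phases at P2D10 dosing. State the convention for Day 10 events without a start time, or refer explicitly to the sponsor's imputation rules if they cover it.
4. Use the P2D10 pre-dose vital sign as the PF-only on-treatment value (against P2D1) and as the PF+OC baseline, and not as a PF+OC post-dose value.

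Laboratory data and ECG can keep the baselines in 3.4. The cost is one extra column in the adverse-event and vital-sign outputs and a few lines of SAP text. No new data, visits or procedures are needed.

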5.3. Methods to Manage Missing Data

For the analysis of safety endpoints, the sponsor data standard rules for imputation will be applied.

5.3.1. Concentrations Below the Limit of Quantification

In all data presentations (except listings), concentrations below the limit of quantification (BLQ) will be set to zero. (In listings BLQ values will be reported as “<LLQ”, where LLQ will be replaced with the value for the lower limit of quantification). For PK calculations, BLQ will be handled by the Pfizer standard processes.

5.3.2. Deviations, Missing Concentrations and Anomalous Values

In summary tables and plots of median profiles, statistics will be calculated having set concentrations to missing if 1 of the following cases is true:

1. A concentration has been collected as ND (ie not done) or NS (ie no sample).
2. A deviation in sampling time is of sufficient concern or a concentration has been flagged anomalous by the pharmacokineticist.

Note that summary statistics will not be presented at a particular time point if more than 50% of the data are missing.

5.3.3. Pharmacokinetic Parameters

Actual PK sampling times will be used in the derivation of PK parameters.

If a PK parameter cannot be derived from a participant's concentration data, the parameter will be coded as NC (ie not calculated). (Note that NC values will not be generated beyond the day that a participant discontinues).

In summary tables, statistics will be calculated by setting NC values to missing; and statistics will be presented for a particular treatment with ≥ 3 evaluable measurements. For statistical analyses (ie, analysis of variance), PK parameters coded as NC will also be set to missing; and analyses will not be performed for a particular parameter if more than 50% of the data are NC.

If an individual participant has a known biased estimate of a PK parameter (due for example to an unexpected event such as vomiting before all the compound is adequately absorbed in the body), this will be footnoted in summary tables and will not be included in the calculation of summary statistics or statistical analyses.

6. ANALYSES AND SUMMARIES

6.1. Primary Endpoint(s)

6.1.1. Pharmacokinetic Endpoints

The mixed effects model described in [Section 5.2](#) will be applied to AUC and C_{max} . The plasma PK parameters in [Table 2](#) will be summarized descriptively by treatment, as applicable, in accordance with Pfizer data standards. AUC_{last} and C_{max} for EE and LN individual participant parameters will be plotted by treatment. Plasma concentrations will be listed and summarized descriptively by nominal PK sampling time and treatment. Individual participant and median profiles of the plasma concentration-time data will be plotted by treatment using actual and nominal times respectively. Median profiles will be presented on both linear-linear and log-linear scales.

Blood samples for PK analysis of EE and LN will be taken according to the Schedule of Activities given in the protocol.

The following PK parameters (shown in Table 6) will be calculated for EE and LN (if possible) from the concentration-time data using standard noncompartmental methods:

Table 6. Noncompartmental PK Parameters

PK Parameter	Analysis Scale	EE	LN
C_{max}	ln, R	A, D	A, D
T_{max}	R	D	D
AUC_{last}	ln, R	A, D	A, D
AUC_{inf}^*	ln, R	A, D	A, D
CL/F^*	R	D	D
PTR	R	D	D
$t_{1/2}^*$	R	D	D

Key: A=analyzed using statistical model, D=displayed with descriptive statistics, ln=natural-log transformed, R=raw (untransformed), NA=not applicable; *=if data permits, C_{max} = Maximum plasma concentration during the dosing interval; T_{max} =Time for C_{max} ; AUC_{last} =Area under the plasma concentration-time profile from time

zero to the time of the last quantifiable concentration (C_{last}); AUC_{inf} = Area under the plasma concentration-time profile from time zero extrapolated to infinite time, and dose normalized AUC_{inf} ; CL/F = Apparent Clearance; PTR = Peak-to-trough ratio; $t_{1/2}$ = Terminal elimination half life.

Table 7. PK Parameters to be Summarized Descriptively by Treatment

Parameter	Summary Statistics
C_{max} AUC_{last} AUC_{inf}^* CL/F^* PTR	N, arithmetic mean, median, $cv\%$, standard deviation, minimum, maximum, geometric mean and geometric $cv\%$.
T_{max}	N, median, minimum, maximum.
$t_{1/2}^*$	N, arithmetic mean, median, $cv\%$, standard deviation, minimum, maximum.

* If data permit.

Box and whisker plots for individual participant parameters (C_{max} , AUC_{last} , and AUC_{inf}) will be presented by treatment (R vs T as described in [Table 4](#)) and overlaid with geometric means. There will be a summary table each for OC (EE and LN) presenting all PK parameters.

Supporting data from the estimation of $t_{1/2}$ will be listed by treatment: terminal phase rate constant (k_{el}); goodness of fit statistic from the log-linear regression (r^2); and the first, last, and number of time points used in the estimation of k_{el} . This data may be included in the clinical study report.

Presentations for OC (EE and LN) concentrations will include:

- A listing of all concentrations sorted by participant ID, period and nominal time postdose. The concentration listing will also include the actual times. Deviations from the nominal time will be given in a separate listing.
- A summary of concentrations by treatment and nominal time postdose, where the set of statistics will include n, mean, median, standard deviation, coefficient of variation (cv), minimum, maximum and the number of concentrations above the lower limit of quantification.
- Median concentration time plot (on both linear and semi-log scales) against nominal time post dose for reference vs test (treatment R vs T as described in [Table 4](#)). Test and reference lines and points will be represented by different colors.

- Mean ($\pm 90\%CI$) concentration time plot (on both linear and semi-log scales) against nominal time post dose for reference vs test (treatment R vs T). Test and reference lines and points will be represented by different colors.
- Individual concentration time plot (on both linear and semi-log scales) against actual time post dose for reference vs test (R vs T [Table 4](#)). Test and reference lines and points will be represented by different colors.
- Individual concentration time plots by treatment (on both linear and semi-log scales) against actual time postdose (there will be separate spaghetti plots for each treatment per scale).
- Individual concentration time plots by participant (on both linear and semi-log scales) against actual time postdose [there will be separate plots for each participant (containing all treatments) per scale].

6.2. Safety Summaries and Analyses

All safety analyses will be performed on the safety population and summarized in accordance with Pfizer Data Standards.

All clinical AEs, SAEs, TEAEs, withdrawal due to AEs, ECGs, vital signs and safety laboratory data will be reviewed and summarized on an ongoing basis during the study to evaluate the safety of participants.

Safety data will be summarized descriptively through appropriate data tabulations, descriptive statistics, categorical summaries, and graphical presentations, where appropriate. Categorical outcomes (eg, AEs) will be summarized by participant counts and percentage. Continuous outcome (eg, blood pressure, pulse rate, etc.) will be summarized using N, mean, median, standard deviation, etc. Change from baseline (CFB) in laboratory data, and vital signs will also be summarized. Participant listings will be produced for the safety endpoints accordingly.

6.2.1. Adverse Events

Adverse events will be reported in accordance with the sponsor reporting standards.

6.2.2. Laboratory Data

Laboratory data will be listed and summarized by treatment in accordance with the sponsor reporting standards. Baseline is as defined in [Section 3.5.2](#).

6.2.3. Vital Signs

Absolute values and changes from baseline in supine systolic and diastolic blood pressure and pulse rate will be summarized by treatment in accordance with the sponsor reporting standards. Tables will be paged by parameter. Baseline is as defined in [Section 3.5.3](#).

Mean changes from baseline with corresponding standard deviations for supine systolic and diastolic blood pressure and pulse rate for each treatment will be plotted against time post-dose. On each plot there will be 1 line for each treatment. Corresponding individual plots of changes from baseline will also be produced for each treatment.

Maximum absolute values and changes from baseline for vital signs will also be summarized descriptively by treatment using categories as defined in [Appendix 1](#). Numbers and percentages of participants meeting the categorical criteria will be provided. All planned and unplanned post-dose timepoints will be counted in these categorical summaries. All values meeting the criteria of potential clinical concern will be listed.

6.2.4. Electrocardiograms

ECG

Absolute values in QT, heart rate, QTcB, QTcF, PR and QRS will be summarized by treatment in accordance with the sponsor reporting standards. Tables will be paged by parameter. Baseline is as defined in [Section 3.5.4](#).

Maximum increase from baseline for QTcB, QTcF, heart rate, QT, PR and QRS will be summarized by treatment in accordance with the sponsor reporting standards.

ECG endpoints (QTcB, QTcF, PR and QRS) will also be summarized descriptively by treatment, using categories as defined in [Appendix 1](#) (for QTc these correspond to ICH E14¹). Numbers and percentages of participants meeting the categorical criteria will be provided. All planned and unplanned post-dose timepoints will be counted in these categorical summaries. All values meeting the criteria of potential clinical concern will be listed.

Listings of participants with any single post-dose value ≥ 500 msec will also be produced for QTcF.

7. INTERIM ANALYSES

No formal interim analysis will be conducted for this study. As this is an open-label study, the sponsor may conduct unblinded reviews of the data during the course of the study for the purpose of safety assessment, facilitating PK/PD modeling, and/or supporting clinical development.

9. APPENDICES

Appendix 1. SAS CODE FOR ANALYSES

An example of the PROC MIXED code is provided below:

```

proc mixed data=tab.pk;
  class trt participant;
  model l&var= trt/ ddfm=KR;
  random participant /participant=participant;
  lsmeans trt /cl alpha=0.1;
  estimate 'Test vs Reference' trt -1 1 /cl alpha=0.1;
  ods 'Estimates' out=est&var;
  ods 'lsmeans' out=ls&var;
  ods 'covparms' out=cov&var;
  ods 'tests3' out=tst&var;
run;

```

/* Letter assignments for treatments (trt) within the estimate statement above are as follows;
(R (OC) = Reference; T (PF-06650833+OC) = Test) */;

Appendix 2. Categorical Classes for ECG and Vital Signs of Potential Clinical Concern

Categories for QTcF

Degree of Prolongation	Mild (msec)	Moderate (msec)	Severe (msec)
Absolute value	>450-480	>480-500	>500
Increase from baseline		30-60	>60

Categories for PR and QRS

PR (ms)	max. \geq 300	
PR (ms) increase from baseline	Baseline >200 and max. \geq 25% increase	Baseline \leq 200 and max. \geq 50% increase
QRS (ms)	max. \geq 140	
QRS (ms) increase from baseline	\geq 50% increase	

Categories for Vital Signs

Systolic BP (mm Hg)	min. <90	
Systolic BP (mm Hg) change from baseline	max. decrease \geq 30	max. increase \geq 30
Diastolic BP (mm Hg)	min. <50	
Diastolic BP (mm Hg) change from baseline	max. decrease \geq 20	max. increase \geq 20
Supine pulse rate (bpm)	min. <40	max. >120

Measurements that fulfill these criteria are to be listed in the clinical study report.

Appendix 3. List of Abbreviations

Abbreviation	Term
AUC _{inf}	area under the plasma concentration-time profile from time 0 extrapolated to infinite time
AUC _{last}	area under the plasma concentration-time profile from time zero to the time of the last quantifiable concentration (C _{last})
BLQ	below the limit of quantification
BP	blood pressure
C _{last}	last quantifiable concentration
C _{max}	maximum plasma concentration during the dosing interval
CFB	change from baseline
CI	confidence interval
CL/F	apparent clearance
CRU	clinical research unit
CV	coefficient of variation
ECG	electrocardiogram
EE	ethinyl estradiol
ICD	informed consent document
ID	identification
k _{el}	terminal phase rate constant
ICH	International Council for Harmonisation of Technical Requirements for Pharmaceuticals for Human Use
LLQ	lower limit of quantitation
LN	levonorgestrel
MR	modified release
NC	Not calculated
ND	not done
NS	no sample
OC	oral contraceptive
PD	pharmacodynamic
PI	principal investigator
PK	pharmacokinetic
PO	by mouth
PTR	peak-to-trough ratio
QD	once daily
QTc	corrected QT
QTcF	corrected QT (Fridericia method)
r ²	the goodness-of-fit statistic from the regression
SAP	statistical analysis plan
SAE	serious adverse event
T _{max}	Time for C _{max}

Abbreviation	Term
$t_{1/2}$	terminal elimination half-life
TEAE	treatment emergent adverse event

PFIZER GENERAL BUSINESS

A large rectangular area of the page is completely blacked out with a redaction marker, obscuring several lines of text.
